8.1 Data and Safety Monitoring Plan

The Data Safety Monitoring Board (DSMB) reviews safety data, study progress, and data quality. The DSMB is chaired by [name], MD (Professor of Pediatrics, Division of Pediatric Cardiology, Vanderbilt Children's Hospital) who is a clinical investigator and practicing cardiac electrophysiologist. Other members are [name], MD (Professor of Medicine, Director of the Division of Cardiac Electrophysiology, VUMC) who is a clinical researcher and has expertise in complex ablation including VT ablation; [name] who is an Anesthesiologist and clinical researcher (Associate Professor of Anesthesiology); and [name], MS (Senior Associate, Department of Biostatistics, VUMC) who has extensive prior experience as a DSMB statistician. The DSMB will review all serious adverse events (AEs). Any serious AE will be reported to the DSMB and IRB within 7 days from the investigators' awareness of the event. Any untoward medical event will be classified as an AE, regardless of its causal relationship with the study. The DSMB reviewed the results of the pilot study and provided input for the Phase II trial and recommended to proceed.

8.2 Reporting of Adverse Events or Unanticipated Problems involving Risk to Participants or Others

Adverse event reporting will utilize the NIH Common Criteria for Adverse Event Reporting (CTCAE version 5.0, published November 2017). It defines an adverse event (AE) as any unfavorable and unintended sign (including an abnormal laboratory finding), symptom, or disease temporally associated with the use of a medical treatment or procedure that may or may not be considered related to the medical treatment or procedure.

Adverse events include:

- Worsening (change in nature, severity or frequency) of conditions present at the onset of the trial
- Patient / subject deterioration due to the primary illness
- Intercurrent illnesses
- Drug interactions
- Events related or possibly related to concomitant medications
- Abnormal laboratory values or changes of vital signs, as well as significant shifts from baseline within the range of normal, which the Investigator considers clinically significant.

Unexpected Adverse Drug Reaction: an unexpected Adverse Drug Reaction is "an adverse reaction, the nature or severity of which is not consistent with the applicable product information (e.g., Investigator's Brochure for an unapproved investigational medicinal product)". Definitions of serious adverse events or serious adverse drug reaction: during clinical investigations, adverse events may occur which, if suspected to be drug-related (adverse drug reactions), must be significant enough to lead to important changes in the way the medicinal product is developed (e.g., change in dose, population, needed monitoring, consent forms). This is particularly true for reactions, which, in their most severe forms, threaten life or function.

A serious adverse event/experience (SAE) or reaction is any untoward medical occurrence that at any dose:

1. results in death
2. is life-threatening
3. requires inpatient hospitalization or prolongation of existing hospitalization
4. results in persistent or significant disability/ incapacity (as per reporter's opinion)
5. is a congenital anomaly/birth defect
6. is another medically important condition
7. The term "life-threatening" in the definition of "serious" refers to an event in which the patient is at risk of death at the time of the event; it does not refer to an event which hypothetically might have caused death if it were more severe.

Important medical conditions that may not result in death, be life-threatening, or require hospitalization may be considered as SAEs when, based upon appropriate medical judgment, they may jeopardize the patient or may require intervention to prevent one of the outcomes listed in the definition above. Examples of such events are intensive treatment in an emergency room or at home for allergic bronchospasm; blood dyscrasias or convulsions that do not result in hospitalization; or development of drug dependency or drug abuse.

Definition of severity of adverse events:

Grades: refer to the severity of the AE. The CTCAE displays Grades 1 through 5 with unique clinical descriptions of severity for each AE based on this general guideline:

- Grade 1 Mild; asymptomatic or mild symptoms; clinical or diagnostic observations only; intervention not indicated.
- Grade 2 Moderate; minimal, local or noninvasive intervention indicated; limiting age appropriate instrumental activities of daily living (ADL).
- Grade 3 Severe or medically significant but not immediately life-threatening; hospitalization or prolongation of hospitalization indicated; disabling; limiting self-care ADL.
- Grade 4 Life-threatening consequences; urgent intervention indicated.
- Grade 5 Death related to AE.

Definition of adverse event causality:

The Investigator will determine causality of each adverse event by using the classification criteria: unlikely, likely, or not assessable.

Unlikely: The AE is considered by the Investigator to be due to a pre-existing condition, a known manifestation of the target disease, a recurrent condition, or is likely explained by environmental or diagnostic therapeutic factors or was pre-existing and did not deteriorate.

Likely: The AE occurred during or after administration of the study treatment or a pre-existing event worsened within an appropriate period of time, and at least one of the following criteria is applicable:

- the event could not be explained by the clinical condition or history of the subject, environmental or toxic factors, or other diagnostic or therapeutic measure;
- was an expected ADR associated with study treatment or a class-labeled drug effect;
- AE subsided or disappeared after withdrawal or dose reduction of study treatment; or
- AE recurred after re-exposure to study treatment.

Not assessable: There is insufficient or conflicting evidence for classifying the causality of the AE as likely or unlikely. Lack of information may apply for this situation.

Note: AEs with causality 'likely' or 'not assessable' are considered to be 'possibly drug-related.'

Adverse event reporting

Any adverse events (AEs) will be reported to the PI within 72 hours of notification of the event. The PI will notify the DSMB of any major adverse events. Any unanticipated problems involving risk to the participants or others will be discussed with the PI and DSMB. Non-serious AEs and incidences of noncompliance with the protocol will be reported to the IRB at the time of annual review.

Serious Adverse Events (SAEs) will be reported according to the following procedure:

The occurrence of serious adverse events will be reported to the Investigator within 24 hours after notification of their occurrence. The Investigator will report SAEs to the DSMB and the Vanderbilt University Medical Center Institutional Review Board within 7 days of the Investigator's notification of the event.

In an unanticipated event of prolonged side effect, requiring prolongation of hospital stay, patients will be retained in the hospital until side effects have resolved. For minor side effects, where inpatient care is deemed unnecessary, follow-up will be maintained via phone or as outpatient if necessary. Patient and their families will be given the PI's contact number for reporting any other effects of medication following discharge.

Any newly discovered information which may affect the subject or their caregiver's decision to continue to participate in the study will be passed on to them as soon as possible. This may also result in a change to the consent form and review by the IRB.

9.0 STUDY WITHDRAWAL AND DISCONTINUATION

A participant may withdraw from the study at any time by informing the study staff verbally or in writing. If an individual withdraws their consent, we will withdraw the participant. Contact information for the PI and study staff will be made available to the participant upon enrollment in the consent document. Any remaining biological samples and data will be destroyed. Any data or biological samples that have been used for research prior to their withdrawal request will not be withdrawn and destroyed.

A participant may be withdrawn from the study by the PI if any of the following occurs:

- i. The participant, for any reason, does not undergo VT or PVC ablation.
- ii. Prior to administration of dantrolene, the participant experiences a complication during the ablation procedure and/or is not considered by the clinical or research team to be clinically stable enough to undergo the research protocol
- iii. Prior to administration of dantrolene, if any of the following criteria are met on the pre-study drug assessment, the research protocol will be stopped, and the study drug will not be administered:
 - a. Mixed venous oxygen saturation (SvO_2) is $<50\%$
 - b. Criteria for RV failure (RA pressure >15 mmHg and CI <2.0 L/min/m 2)
 - c. Criteria for severe pulmonary hypertension (PA systolic pressure ≥60 mmHg)
- iv. The participant experienced an adverse event related to the study drug/protocol.

Conduction Time: is a continuous measurement. To most accurately measure conduction time, it is the mean value of multiple measurements along the horizontal aspect of the conduction curve (**Figure 7**). Conduction time is analyzed separately for the low voltage and higher voltage areas. Multivariable linear regression models will be built. Simple linear regression models will be used to test whether treatment with dantrolene is associated with a statistically significant decrease in mean post-drug conduction time when adjusted for mean pre-drug conduction time. Multivariable linear regression models will include additional adjustment for age, sex, mean bipolar voltage, amiodarone exposure (yes/no), change in beta-agonist exposure, and time from start of drug to post-drug EPS. Mean bipolar voltage will be the mean of the peak electrogram measured on the recording electrode for each of the extrastimuli.

Effective Refractory Period: is a continuous measurement. The ERP is measured at within the low voltage area and higher voltage areas at a drive train of 600 ms. It is measured pre-study drug and post-study drug. Multivariable linear regression models will be built. Separate models will be built for the low and higher voltage areas. Simple linear regression will test whether treatment with dantrolene is associated with a statistically significant increase in mean post-drug ERP when adjusted for mean pre-drug ERP. Multivariable analysis will be conducted using the same methods as described for conduction time.

Secondary Analyses Aim 1: activation time and conduction restitution are additional metrics for conduction. They are analyzed with the same statistical approach as described for conduction time.

Sample Size and Power Aim 1: The primary endpoints are conduction time and ERP. Pre- and post-drug difference in average conduction time and ERP will be compared between the dantrolene and the placebo group. We expect the conduction time to decrease and ERP to increase substantially after drug in the treatment arm, while no change is expected in the placebo arm. With 56 patients treated with dantrolene and 28 placebos, there will be 80% power to detect a $0.6 \times SD$ difference in the average conduction time and the average ERP change between the two study arms.

Hemodynamic Endpoints: The primary hypothesis in Aim 2 tests whether RyR2 inhibition increases cardiac output and decreases PA diastolic pressure in patients with structural heart disease. The primary endpoints are cardiac index and mean PA diastolic pressure. Secondary endpoints are RA and PA pressures, RV stroke volume index, PA pulsatility index, and systemic and pulmonary vascular resistances.

Primary Analysis (Aim 2): Our primary analyses use multivariable linear regression to test whether our primary determinant (dantrolene vs. placebo) is associated with: 1) post-drug mean cardiac index and 2) post-drug mean PA diastolic pressure. Adjustment is made for pre-study drug measurements. Additional adjustment in the multivariable model includes: age, sex, LV ejection fraction (continuous), change in beta-agonist exposure, ventricular arrhythmia induced (yes/no), and time from start of study drug to post-drug hemodynamic measurements. Mixed-effect models with linear regression will be built for the repeated measurements to account for the correlation structure in the data, where patient ID will be treated as a random effect. Fixed effect factors include treatment arm, measurement time (1,2,3, etc.), and all covariates. The cardiac index and PA diastolic pressure adjusted for pre-drug measurements is presented for both treatment arms, together with corresponding 95% confidence intervals (CIs) and p-values are graphically interpreted using boxplots, partial effect plots, residual plots, etc.

Secondary Analysis (Aim 2): Secondary endpoints are RA and PA pressures, PA pulsatility index, and systemic and pulmonary vascular resistances. They are analyzed with the same statistical approach as described for output and PA diastolic pressure.

Sample Size and Power Aim 2: The pre- and post-drug difference in average cardiac index and PA diastolic pressure will be compared between the dantrolene and the placebo group. We expect the cardiac output to increase and PA diastolic pressure to decrease substantially after drug in the treatment arm, while no change is expected in the placebo arm. However, to allow for unexpected effects (e.g. negative inotropy), two-sided tests will be performed. With 56 patients treated with dantrolene and 28 with placebo, the study will provide 80% power to detect a $0.6 \times SD$ difference in the average cardiac index and the average PA diastolic pressure change

between the two study arms. For instance, if the pre-drug PA diastolic pressure measurements have a SD of 4 mmHg, we will have 80% power to detect a difference of +/- 2.4 mmHg in PA diastolic pressure. If the pre-drug average PA diastolic pressure is 12 mmHg, this means a 20% change in the treatment arm is detectable assuming there is no change in the control arm. Each primary endpoint will be tested at the two-sided 5% significance level.

Inducibility Endpoints: The primary hypothesis in Aim 3 tests whether RyR2 inhibition with dantrolene reduces the susceptibility to ventricular arrhythmias. Susceptibility to ventricular arrhythmias is measured by testing the inducibility of VT/VF using programmed ventricular stimulation.

Primary Analysis Aim 3:

Inducibility of Ventricular Arrhythmias: Ventricular arrhythmias are defined as monomorphic or polymorphic VT, or VF. The primary endpoint is either a sustained hemodynamically stable ventricular arrhythmia of ≥ 10 seconds duration or an unstable ventricular arrhythmia requiring termination (with pacing or defibrillation), or two episodes of non-sustained ventricular arrhythmia defined as an episode lasting 3-9 seconds. To maximize statistical power, the primary analysis utilizes an ordinal endpoint that measures the relative inducibility based on the stage of the induction protocol and the arrhythmia induced (**Table 5**). Multivariable regression models are built. Univariable logistic regression modeling will be used to test whether treatment with dantrolene is associated with the category of inducibility (ordinal endpoint) measured post-study drug with adjustment for the stage of inducibility measured pre-study drug. Multivariable modeling includes additional adjustment for age (continuous), sex, amiodarone exposure (yes/no), change in beta-agonist exposure, and time from start of drug to post-drug stimulation protocol. Models will be evaluated for goodness-of-fit, and internally validated for calibration/discrimination with bootstrap.

Secondary Analyses Aim 3: A binary endpoint of inducibility (yes/no) is analyzed using logistic regression with the same covariate adjustment described for the primary analysis. Another secondary analysis tests the idea that RyR2 inhibition with dantrolene may alter inducible ventricular arrhythmias due to changes in conduction and refractoriness and hemodynamic improvement. An ordinal variable defining the cardiac rhythm stability class is analyzed (**Table 6**) using multivariable ordinal logistic regression. A secondary analysis will explore all the ventricular arrhythmia susceptibility endpoints for an interaction between cardiomyopathy type (ischemic versus non-ischemic) and treatment with dantrolene. Definitions: 1) Stable monomorphic VT is mean arterial pressure at 10 seconds (MAP_{10}) or immediately prior to termination of >50 mmHg; 2) Unstable VT is MAP_{10} or prior to termination of <50 mmHg; 3) Pleomorphic VT is more than one QRS morphology for 3 or more consecutive beats during the same VT episode; and 4) Polymorphic VT is a continually changing QRS morphology.⁵⁴

Sample Size and Power Aim 3: Primary Endpoint: The sample size selected for this trial was calculated to adequately power the analysis of the inducibility endpoint in Aim 3 which is an ordinal variable (Table 5). With $N=84$ patients (randomized to placebo and treatment in 1:2 ratio) with an expected 50% of patients in the placebo arm non-inducible, and 10% in each of the other categories, the study will achieve 80% power to detect an odds ratio (OR) of 0.3 at the two-sided significance level of 5%. With an anticipated 20% withdrawal rate prior to study drug, up to a total number of 105 patients will be enrolled in the study to ensure statistical power. Secondary Endpoints: 1) The binary status of inducibility (yes/no). With an effective sample size of 84, the study provides 80% power to detect an OR of 0.25, and a 70% power to detect an OR of 0.3 at the two-sided significance level of 5%.

Assessment of Safety (Aim 3): An interim analysis will be performed by the DSMB when 50% of the target enrollment is reached to test for an association between dantrolene or placebo and significant adverse events/harm. In order to preserve statistical power for the secondary analyses, the interim analysis will not include early stopping rules for efficacy. Although none of our Phase I pre-clinical or clinical data have raised

Table 5. Ordinal Inducibility Endpoint

	Category	
Least inducible	0	No sustained VT/VF or NSVT
	1	1 episodes of NSVT with S4
↓	2	1 episodes of NSVT with S3
↓	3	1 episodes of NSVT with S2
↓	4	2 episodes of NSVT with S4*
↓	5	2 episodes of NSVT with S3*
↓	6	2 episodes of NSVT with S2*
↓	7	Sustained VT/VF with S4
Most inducible	8	Sustained VT/VF with S3
	9	Sustained VT/VF with S2

*the category assigned for 2 episodes of NSVT is based on the extrastimulus used to induce the second episode of NSVT.

Table 6. Secondary analysis of rhythm stability

	Category	
Least Stable	1	Ventricular Fibrillation
	2	Polymorphic VT
↓	3	Pleomorphic VT
↓	4	Unstable Monomorphic VT
Most Stable	5	Stable Monomorphic VT
	6	No Inducible VT/VF

safety concerns, and no adverse events have been observed, we planned the assessment of safety, which will be based on the frequency of adverse events. Other safety data such as blood pressure will be considered. All adverse events recorded during the study will be summarized. See Ethical Aspects of the Proposed Research for DSMB.

Respiratory Mechanics and Ventilation Endpoints: To monitor adequacy of ventilation, maintain safety, and measure the effect of dantrolene administration on ventilation, the anesthesiologist will monitor respiration and oxygenation as is standard of care for all patients during procedures and surgeries. The primary endpoint of the Respiratory Mechanics substudy is the incidence of the addition of respiratory support, including bag/mask ventilation, CPAP, BiPAP, LMA, or tracheal intubation, from the time of study drug administration until 120 minutes after study drug administration. Placement of airway support devices is at the discretion of the attending anesthesiologist and will be based on standard safety parameters such as oxygen saturation, adequacy of ventilation, and airway obstruction. Secondary endpoints include additional markers of respiratory mechanics and strength including negative inspiratory force, dynamometer measured grip strength, accelerometer (respiratory rate, tidal volume, minute ventilation), markers of gas exchange (arterial pH, pCO₂, pO₂, base excess), and electrolytes. Tidal volume, respiratory rate, and minute ventilation parameters will be continuously collected (recorded every minute) as available. We will summarize these data prior to study drug administration and at 10 and 20-minutes after dantrolene administration.

Prior to the ablation procedure and administration of anesthesia, a baseline negative inspiratory force (NIF) will be collected x3 in the supine position. A repeat NIF measurement will be again collected in the PACU 2 hours post dantrolene administration and then again at 24 hours. We will summarize NIF data prior to and following dantrolene administration.

Arterial blood gas (ABG) sampling will be performed at four time points: intraoperatively just prior to dantrolene administration, 10- and 20-minutes post dantrolene administration, and 2 hours post dantrolene administration in the PACU. ABG sampling will allow sampling of respiratory mechanic parameters including pH, pCO₂, pO₂, and base deficit/excess. We will summarize ABG data at these four timepoints.

Muscle Strength Endpoints: We will assess grip strength as measured with a handheld dynamometer x3 prior to the ablation procedure and administration of anesthesia and 2 hours following dantrolene administration and then again at 24 hours. We will summarize these data.

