6.6 Ventricular Arrhythmia Induction Protocol

A standardized induction protocol is performed using programmed ventricular stimulation from the RV apex. The protocol is based on a prior study evaluating a range of induction protocols used to test inducibility before and after AAD administration in the EP lab.³⁹ Sedation and vasopressor infusion is maintained at constant levels throughout the study protocol and, any changes warranted for clinical care will be documented. The pacing cycle length is 8 beats followed by extrastimuli (ES) and a 3 second rest period. The basic cycle length of the pacing drive train (S1 – S1) is 600 ms (100 bpm). The first extrastimulus (S2) is introduced at 300 ms and decremented by 10 ms to VERP or 200 ms. S2 is then set to a coupling interval (S1 – S2) of VERP (or 200 ms) + 20 ms and a second extrastimulus (S3) added at a coupling interval of S1-S2 + 50 ms and scanned to refractoriness or a minimum coupling interval of 200 ms. The second extrastimulus is then set to its VERP + 20 ms and a third extrastimulus (S4) added at an initial coupling interval (S3 – S4) of S2 – S3 + 50 ms and scanned in to refractoriness or 200 ms. Thus up to 3 extrastimuli are added and the minimum coupling interval will not be shorter than 200 ms. The induction protocol is stopped when: 1) the primary endpoint is met, or 2) the induction protocol has been completed. The primary endpoint is an episode of sustained VT that lasts \geq 10 seconds or two episodes of non-sustained ventricular arrhythmia defined as VT or VF that lasts 3-9 seconds.

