6.9 Arterial Blood Pressure Measurement

As part of an ablation procedure, invasive arterial blood pressure is monitored via an arterial pressure catheter (femoral and/or radial artery). As clinical endpoints, systolic, diastolic, mean and pulse pressures are recorded immediately prior to study drug administration, and then every 2 minutes after drug administration during the research protocol (except during pacing maneuvers). Changes in vasopressor infusion rate and boluses are also recorded.

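### The Aim 2 primary model adjusts for change in beta-agonist exposure, probably a post-drug quantity, leaves the timing of induced arrhythmia unstated, and omits both randomisation strata

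*Combined protocol and SAP*

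**What the plan says.** All references are to the combined protocol and SAP. Aim 2 here means the hemodynamic aim as numbered in Section 10.0, with cardiac index and PA diastolic pressure as primary endpoints.

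- **Primary analysis.** Section 10.0, Primary Analysis (Aim 2): "Our primary analyses use multivariable linear regression to test whether our primary determinant (dantrolene vs. placebo) is associated with" the two post-drug means. The model adjusts for the pre-drug measurement, age, sex and continuous LVEF, and also for "change in beta-agonist exposure, ventricular arrhythmia induced (yes/no), and time from start of study drug to post-drug hemodynamic measurements". No window is given for the beta-agonist term and no timing for the arrhythmia term. The mixed model for repeated measurements carries the same covariates.
- **Baseline-adjusted results.** The same paragraph adds: "The cardiac index and PA diastolic pressure adjusted for pre-drug measurements is presented for both treatment arms", with confidence intervals and p-values. It does not say that this is the result that decides.
- **Vasopressors.** Section 6.6: "Sedation and vasopressor infusion is maintained at constant levels throughout the study protocol and, any changes warranted for clinical care will be documented". Section 6.9, on the blood pressures taken before and after study drug: "Changes in vasopressor infusion rate and boluses are also recorded".
- **Stimulation.** Programmed stimulation is done before and again after study drug. Table 2 and Section 6.2 both list post-drug hemodynamics before post-drug stimulation.
- **Strata.** Section 5.0 stratifies randomisation by amiodarone use and by planned PVC versus VT ablation. Neither is in the Aim 2 model. PVC versus VT is in no listed efficacy model; amiodarone is in the fuller Aim 1 and Aim 3 models.
- **Aims 1 and 3.** Each plans a model adjusted only for the pre-drug value and a fuller one. The plan does not say which decides.

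**The concern.** Randomisation protects the comparison of arms only while the model conditions on things fixed before treatment. A change covariate in a model for a post-drug outcome most naturally describes what happened during the protocol, and vasopressor changes are recorded in that period. The plan itself allows that dantrolene might affect hemodynamic support: "to allow for unexpected effects (e.g. negative inotropy), two-sided tests will be performed". If it does, the primary coefficient answers what dantrolene does at an equal change in agonist exposure, which is not the Aim 2 hypothesis.

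Induced arrhythmia raises a different problem. Two analysts could take the pre-drug or the post-drug test and fit different primary models. The first is a baseline covariate. The second is the Aim 3 outcome, and on the plan's own assumptions it would differ by arm.

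The strata matter less. A model that ignores factors used to balance the arms reports a somewhat larger standard error than it needs to.

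**Working it through.** **Inputs from the documents.** 56 dantrolene and 28 placebo; two-sided 5% per endpoint; target difference 0.6 SD; example SD 4 mmHg for pre-drug PA diastolic pressure; for Aim 3, "expected 50% of patients in the placebo arm non-inducible" and, for binary inducibility, "the study provides 80% power to detect an OR of 0.25, and a 70% power to detect an OR of 0.3". **Assumed:** every slope, the arm difference in beta-agonist change, any pre-post correlation, and the share of variance explained by the strata.

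**The plan's own power figure.** k = √(1/28 + 1/56) = 0.2315. Two-sample power at 0.6 SD is Φ(0.6/0.2315 − 1.96) = Φ(0.632) = 73.6%, against the stated 80%. Adjusting for a pre-drug value with correlation of about 0.38 would give 80%; the plan states no correlation. This is a separate matter and does not bear on the point.

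**Beta-agonist change.** Let d be the between-arm difference in the covariate (in SD) and s the within-arm slope of the outcome on it (SD per SD). Then

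adjusted coefficient − total effect = −s × d.

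Under a true total effect of zero, and without the pre-drug value in the model, the standard error is about √(1 − s²) × k. At s = ±0.5 this is 0.866 × 0.2315 = 0.200.

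| Arm difference d | Bias at s = ±0.5 | Bias / SE | Type I error |
|---|---|---|---|
| 0 | 0 | 0 | 5.0% |
| 0.1 SD | ∓0.05 SD | 0.25 | 5.7% |
| 0.2 SD | ∓0.10 SD | 0.50 | 7.9% |

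Simulation of 20,000 trials per cell agrees: across slopes from −0.5 to +0.5, type I error was 4.9 to 6.2% at d = 0.1 and 5.3 to 7.8% at d = 0.2. On the plan's 4 mmHg example, 0.05 to 0.10 SD is 0.2 to 0.4 mmHg, against a target of 2.4 mmHg.

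These error rates omit the pre-drug value that the plan requires. Adding it does not change −s × d if s is held fixed, but it shrinks the standard error. At an assumed correlation of 0.6 and s = ±0.5, the standard error is √(1 − 0.36 − 0.25) × 0.2315 = 0.145. Type I error becomes 6.4% at d = 0.1 and 10.6% at d = 0.2. The error rates are illustrations, not properties of this trial.

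**Induced arrhythmia.** If pre-drug, it is balanced by randomisation and d = 0 in expectation, so there is no distortion; simulation with s = −0.5 gave −0.001 for a true 0 and 0.602 for a true 0.6. If post-drug, the plan's figures give 50% induced on placebo. On dantrolene, where the placebo odds are 1, the proportion is OR/(1 + OR): 0.25/1.25 = 20.0% or 0.30/1.30 = 23.1%. The arm difference is 27 to 30 percentage points. An assumed slope of ±0.2 SD then gives a distortion of about 0.05 to 0.06 SD in size; ±0.5 SD gives about 0.13 to 0.15 SD; a slope of 0 gives none.

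**Strata.** If they explain a share R² of the variance left by the other covariates, omitting them widens the standard error by 1/√(1 − R²): 1.010 at 2%, 1.026 at 5%, 1.054 at 10%, 1.085 at 15%. In simulation (amiodarone 50%, PVC 30% and blocks of 3 or 6, all assumed) estimates stayed unbiased at 0.599 to 0.602 for a true 0.6. Type I error was 4.7% at R² of 1 to 2%, falling to 3.7% at 15%, so the test is slightly conservative.

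**The case against.** The case for leaving the model alone has weight. Section 6.6 holds vasopressors constant apart from clinically needed changes, and nothing in the documents equates vasopressors with beta-agonists. No arm difference is reported. The plan calls a negative inotropic effect unexpected, Section 3.2 reports no significant vital-sign changes in healthy volunteers, and Section 1.4 cites cardiomyocyte data without reduced contractility. With no arm difference there is no bias. All this limits the likely size. It does not define the covariate or make it a baseline one.

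The order of procedures favours the pre-drug reading of induced arrhythmia, because a covariate meant to explain a hemodynamic reading should precede it. That stands, and it is why the larger distortions above are conditional on the less natural timing. A post-drug arrhythmia would mostly not be a mediator of readings already taken, though conditioning on a later outcome of treatment can still distort the comparison.

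Baseline-adjusted results are to be presented with p-values, so an estimate free of the contested terms may already be reported. That is fair, but the same paragraph labels the multivariable model primary.

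A reader might infer that the Aim 2 result will be biased, or that the model will cost a stated amount of power. The documents support neither. The size and sign of any bias are unknown, and a power figure would rest on an assumed slope and an unstated pre-post correlation. Nor do the documents support reading the omitted strata as a source of bias in the linear models.

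**Conclusion.** The point holds in a conditional form and should be fixed. The plan gives primary status to a model containing one covariate that is probably measured after study drug and one whose timing is open, and it names no decisive Aim 2 model without them. For beta-agonist change, the bias is zero if exposure does not differ by arm and up to 0.05 to 0.10 SD under the assumed differences and slopes, with type I error of about 5 to 8% in a model without the pre-drug value. For induced arrhythmia there is no harm if it is pre-drug; if post-drug, it is an outcome of treatment and should not be adjusted for. Leaving out the strata costs about 1 to 3% in standard error at an R² of 2 to 5%, and nothing if they are not prognostic. Confidence is high that the terms are undefined and the deciding model unnamed; whether the result would in fact be distorted cannot be judged from the documents. Aims 1 and 3 are less affected, because a pre-drug-adjusted model is already planned there.

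**What to change.** **Aim 2.**
- Make the decisive model treatment arm, pre-drug value, both randomisation strata, age, sex and LVEF, and use the same covariates in the mixed model.
- If arrhythmia status is kept, specify the pre-drug result.
- Define beta-agonist exposure (which agents, what measure) and its window. Move its change to a labelled supportive analysis and report it by arm.
- Time from study drug to measurement is also fixed after dosing and can go in the supportive model; no bias is claimed for it.

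**Aims 1 and 3.** Add the two strata to the pre-drug-adjusted model already planned and state that it decides. The fuller models can stay as they are, as supportive analyses.

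**Cost.** SAP wording and one or two degrees of freedom. The strata are known at randomisation and vasopressor changes are already recorded, so no new procedure is needed. Dropping beta-agonist change from the decisive model may lose a little precision if it predicts the outcome.
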